#### *11.3.2.7. Weeks 6, 8 and 10*

Subject will continue to be dosed once daily.

On day 42, 56 and 70 ( $\pm 1$  day) the following procedures will be performed:

- Growth Assessment
- Fecal sample

#### *11.3.2.8. End of Dosing/Hospital Discharge*

Dosing will continue until a post-conception age of 34 weeks, or until hospital discharge, whichever comes first. If a subject stops study drug dosing prior to the post-conception age of 34 weeks, the following procedures will be completed on the day the subject receives his/her last dose of blinded study treatment:

- Physical examination
- Vital Signs
- Growth Assessment
- Fecal sample
- Assessment of AEs
- Assessment of concomitant medication changes

Discharge evaluations will be performed by a physician-Investigator who is a board-certified staff neonatologist and be performed per standard NICU practice.

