**Figure 1: Treatment Group Sequence**

All neonates enrolled will receive daily doses of blinded study treatment through 34 weeks of post-conceptual age or neonatal intensive care unit (NICU) discharge, whichever comes first. While in the NICU, neonates will be evaluated daily for signs/symptoms of NEC, feeding volumes/feeding tolerance, AEs, and concomitant medications. Physical examinations and vital signs will be performed daily during the dosing period and at the end of dosing/NICU discharge. Growth assessments will be performed every other week while in the NICU and at the end of dosing/NICU discharge. Assessments for complications of prematurity, including retinopathy of prematurity (ROP), intraventricular hemorrhage (IVH), and bronchopulmonary dysplasia (BPD) will be

performed at protocol defined timeframes (see [Section 11.2](#)). Neonates enrolled in the study will have fecal/meconium samples collected daily through 4 days following the start of dosing and weekly thereafter until NICU discharge to determine fecal shedding of [REDACTED] (STP6) and [REDACTED] (STP11).

Following completion of blinded study treatment dosing, neonates will be evaluated at 1 week, 1 month, 3 months, and 6 months for safety and growth assessments.

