## **9. STUDY POPULATION**

### **9.1. Number of Subjects**

The study will be conducted at up to 20 active centers.

This study will require at least nine evaluable neonates (*i.e.*, completing minimum dosing duration described in [Section 11.3.2](#) and having a post-dosing assessment performed) per treatment group for each of the eight treatment groups. It is not expected that there will be a high percentage of neonates that do not meet evaluability criteria. Thus, to achieve the required number of evaluable neonates, it is anticipated that approximately 100 to 110 neonates will be enrolled in this study.

There are no limitations on the number of subjects that may be enrolled at each center.

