## **10.8. Study Medication Administration and Compliance**

### 10.8.1. Dosage and Administration

Dosing of blinded study drug will be initiated within 4 days (i.e., 96 hours) after birth. Dosing is intended to consist of a single daily bolus dose administered as part of a scheduled feeding. However, in neonates who are volume restricted, the total daily dose may be divided and given twice daily (BID) or three times daily (TID) until full amount can be tolerated in one dose. In neonates where the dose volume is less than the maximum volume tolerated, dosing may be supplemented with regular feeding. In neonates receiving continuous feeds, the feed will be interrupted for dose administration and then immediately restarted. The date, time and volume of each dose administration will be recorded.

In neonates who are still on tube feeds, the dose will be given by feeding tube prior to feeding. If dosing at the time of feeding is not possible, the dose may be given and then the line flushed with sterile water to assure delivery of the full dose. In larger neonates who feed orally by breast or bottle for all feeds and do not have a feeding tube in place, the dose will be fed directly into the mouth before a feed using a syringe intended for oral drug administration. In the event the dose is spit up, the neonate will not be re-dosed. Regurgitation of the dose will be noted in the source document and the case report form.

Prior to administration, subject identification will be verified against the labeled syringes to ensure that the correct IP is given.

The times of product reconstitution and dose administration will be recorded. Reconstituted components of STP206 should be administered within 2 hours following reconstitution.

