### 11.3.2. Dosing Duration

The subject’s gestational age at birth will dictate how many weeks of dosing will be administered as outlined in the table below. For the initial 2 weeks of daily dosing, neonates should not miss more than 2 doses per week. It is intended that neonates receive blinded study treatment for between 2 to 11 weeks based upon the protocol-defined gestational age. However, in the event of early hospital discharge, the minimum required dosing duration is provided in [Table 2](#).

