**Table 2: Dosing Duration Guidelines**

Gestational Age at Birth	Protocol Defined Gestational Age	Intended Dosing Duration Weeks (Days)	Minimum Required Cumulative Dosing Days a,b
23 weeks 0/7 days to 23 weeks 6/7 days	23 weeks	11 (77)	54
24 weeks 0/7 days to 24 weeks 6/7 days	24 weeks	10 (70)	49
25 weeks 0/7 days to 25 weeks 6/7 days	25 weeks	9 (63)	45
26 weeks 0/7 days to 26 weeks 6/7 days	26 weeks	8 (56)	40
27 weeks 0/7 days to 27 weeks 6/7 days	27 weeks	7 (49)	35
28 weeks 0/7 days to 28 weeks 6/7 days	28 weeks	6 (42)	30
29 weeks 0/7 days to 29 weeks 6/7 days	29 weeks	5 (35)	25
30 weeks 0/7 days to 30 weeks 6/7 days	30 weeks	4 (28)	20
31 weeks 0/7 days to 31 weeks 6/7 days	31 weeks	3 (21)	15
32 weeks 0/7 days to 32 weeks 6/7 days	32 weeks	2 (14)	10

a. Over the first 2 weeks of dosing, neonates should receive study drug for a minimum of 5 of the 7 dosing days, per week

b. ≥70% of intended dose

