Post Dosing 6 Month ^d	181 to 195 days	181 <= (assessment date – expected last dose date+1) <= 195 days
Post Dosing 18 Month/End ^d	Not specified	520 <= (assessment date – expected last dose date+1) <= 576 days
Withdrawal Prior to Post Dosing 6 Month ^d	Not specified	assessment date >= date of withdrawal and (assessment date – expected last dose date+1) <= 181 days
Withdrawal between Post Dosing 6 and 18 Month ^d	Not specified	assessment date >= date of withdrawal and 196 days < (assessment date – expected last dose date+1) < 520 days

- a- Windows for vital sign measurements and physical examinations.
- b- Window for fecal sample.
- c- Window for IVH measurement.
- d- Windows for growth assessment (note that Post Dosing 18 Month data will only be presented in listings).
- e- Windows for Post Dosing may be adjusted to account for patients that terminated dosing early. For example, if a subject early terminates dosing at Week 10 but was expected to complete dosing at Week 11, then the Post Dosing window will be adjusted to reflect planned time point after expected dosing completion.

If a subject has more than 1 assessment occurring in the same visit window, the data from the visit closest to the scheduled study day will be used for summaries. If two assessments have the same distance from the scheduled study day, the assessment after the scheduled study day will be used for the analyses.

If multiple assessments occur as Baseline (screening or Day 1 prior to dosing), then the last assessment before the first study dose will be used for the analyses.

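### The 34-week stop and Table 2 give end-of-dosing dates up to 10 days apart, which leaves evaluability at 30 to 32 weeks and the SAP's expected last dose date open to interpretation

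*Protocol*

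**What the plan says.** **An age-based end.** Protocol 11.3.2.8: "Dosing will continue until a post-conception age of 34 weeks, or until hospital discharge, whichever comes first". Protocol 7.1 gives daily dosing "through 34 weeks of post-conceptual age or neonatal intensive care unit (NICU) discharge, whichever comes first". SAP 4.1 and 6.2.3 repeat the 34-week end.

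**A fixed-duration end.** Under Protocol 11.3.2 the infant's "gestational age at birth will dictate how many weeks of dosing will be administered as outlined in the table below", and "It is intended that neonates receive blinded study treatment for between 2 to 11 weeks based upon the protocol-defined gestational age". Table 2 has one row per completed week. The row "32 weeks 0/7 days to 32 weeks 6/7 days" carries 14 intended days and a minimum of 10. The footnote on the minimum says 70% in the protocol and 75% in SAP 6.2.3, above the same tabled day counts.

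**Start of dosing.** Protocol 10.8.1: "Dosing of blinded study drug will be initiated within 4 days (i.e., 96 hours) after birth".

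**Use of the minimum.** Protocol 9.1: "This study will require at least nine evaluable neonates" per group, where evaluable means completing the minimum dosing duration and having a post-dosing assessment. Protocol 9.5.3 and SAP 7.3 base replacement on the same minimum, and SAP 8.3.3 bases the per-protocol set on it.

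**Use of the end date.** SAP 6.2.2 (Table 4) counts post-dosing windows from an expected last dose date. No formula is given. Footnote e says that if dosing ends early, "then the Post Dosing window will be adjusted to reflect planned time point after expected dosing completion".

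**The concern.** Table 2 treats every infant in a row as if born on day 0 of that week and dosed from the day of birth. An age-based stop does not. An infant born late in the week who starts on day 4 therefore has fewer dosing days before 34 weeks than Table 2 assumes.

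Two things are at stake. First, an infant dosed to 34 weeks has completed treatment by the definitions in Protocol 7.1.3.1, yet could fall below the Table 2 minimum. That infant would be non-evaluable, would count towards replacement, and could be left out of the per-protocol set without any departure from the dosing text. Second, visits scheduled from the actual last dose may fall outside SAP windows counted from a different expected date.

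**Working it through.** **Inputs.** w = completed gestational week at birth (Table 2, 23 to 32); d = extra days, 0 to 6 (Table 2 row limits); s = days from birth to first dose, 0 to 4 (Protocol 10.8.1). This gives 7 × 5 = 35 combinations per row. No missed doses or early discharge are assumed; either would shorten dosing further.

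**Step 1: reproduce Table 2.** Intended days = 7 × (34 − w), for example 7 × (34 − 32) = 14 and 7 × (34 − 23) = 77. Minimum = 70% of intended, rounded up: 0.70 × 14 = 9.8, so 10; 0.70 × 77 = 53.9, so 54. All ten rows match. The SAP's 75% does not reproduce them: it gives 11 rather than 10 at 32 weeks (0.75 × 14 = 10.5) and 58 rather than 54 at 23 weeks (0.75 × 77 = 57.75).

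**Step 2: days available under an exact-age stop.** Available = 7 × (34 − w) − d − s if the last dose precedes 34w0d; add 1 if 34w0d is dosed.

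| w | Intended | Minimum | Available, last dose before 34w0d | Short of minimum | Available, 34w0d dosed | Short of minimum |
|---|---|---|---|---|---|---|
| 29 | 35 | 25 | 25–35 | 0/35 | 26–36 | 0/35 |
| 30 | 28 | 20 | 18–28 | 3/35 | 19–29 | 1/35 |
| 31 | 21 | 15 | 11–21 | 10/35 | 12–22 | 6/35 |
| 32 | 14 | 10 | 4–14 | 20/35 | 5–15 | 15/35 |

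No combination falls short at 23 to 28 weeks. With the last dose before 34w0d, the full intended days fit in 1 of 35 combinations in every row (d = 0, s = 0).

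**Step 3: gap between the two end dates.** Gap = d + s, at most 6 + 4 = 10 days, or 9 if 34w0d is dosed. Example: birth at 32w6d with first dose on day 4 starts dosing at 33w3d. The last dose before 34w0d is at 33w6d (4 doses); the 14th dose of Table 2 would fall at 35w2d.

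**Step 4: other readings of the 34-week stop.**
- Age counted from the protocol-defined (completed) week: available = 7 × (34 − w) − s. At 32 weeks this is 10 to 14 days, no row falls short, and the gap is at most 4 days.
- Exact age, dosing through 34w6d: available = 7 × (34 − w) − d − s + 7. At 32 weeks this is 11 to 21 days and no row falls short, though the total still differs from Table 2.

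**Step 5: visit windows.** A visit x days after the actual last dose, with the expected date k days later, has SAP day x − k + 1. The protocol's 1-week visit is x = 5 to 9; the SAP window is days 6 to 13.
- k = 0: SAP days 6 to 10, so 5 of 5 are inside.
- k = 4: SAP days 2 to 6, so 1 of 5.
- k = 5: SAP days 1 to 5, so 0 of 5, and 0 for any larger k.

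With k = d + s, k ≥ 5 in 20 of 35 combinations in any row (15 of 35 if 34w0d is dosed and k = d + s − 1). At k = 10, 6 of 15 protocol days remain inside at 3 months and at 6 months, against 14 of 15 at k = 0. The 1-month window is not harmed (6 of 6).

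**The case against.** The strongest reply is that Table 2 is itself a 34-week rule. Every intended duration is 7 × (34 − completed week), and Protocol 11.3.2 ties duration to the protocol-defined gestational age. Counted that way, a 32-week infant starting on day 4 still has 14 − 4 = 10 days, exactly the minimum. Several passages also say through rather than until 34 weeks, which can mean 34w6d. Under either reading, or if Table 2 simply governs, no infant is barred from the minimum. This stands, so the shortfall is conditional. It does not remove the conflict, because the documents select none of these readings, and the first leaves a 32-week, day-4 starter no room for a missed dose although Protocol 11.3.2 allows up to two a week in the first two weeks.

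The consequences are also bounded:
- Small-for-age infants are excluded, and Appendix D's 10th percentile at 30 weeks is 1,052 g (girls) and 1,114 g (boys). Eligible 30 to 32 week infants therefore fall only in the 2000–1501 g and 1500–1000 g strata; the four lighter groups are unaffected by the shortfall.
- Replacement begins only after more than three infants in a group fall short, and replaced infants stay in the ITT and Safety analyses (SAP 7.3).
- SAP 8.6 analyses efficacy in ITT only. SAP 8.3.3 promises repeat per-protocol analyses, but the per-protocol tables listed are baseline characteristics.
- The post-dosing windows carry the growth-assessment footnote, so the effect is mainly on a descriptive growth table. The primary adverse event endpoint runs from the last dose itself. Footnote e's Week 10 versus Week 11 example leans towards planned weeks, although SAP 6.2.3 says through 34 weeks.

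**Conclusion.** The end-of-dosing passages conflict and need to be reconciled. The two end dates differ by up to 10 days, and the SAP does not say which of them defines the expected last dose date.

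The shortfall against the minimum (15–20, 6–10 and 1–3 of 35 combinations at 32, 31 and 30 weeks) rests on one reading: exact gestational age with a stop at 34w0d. The range reflects whether 34w0d is dosed. The window effect rests on the expected date being the Table 2 date while dosing stopped at 34w0d.

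A reader might infer that many 31 to 32 week infants cannot become evaluable, for instance by turning 15–20 of 35 into 43–57% of 32-week infants. The documents do not support that. They give no distribution of birth days or start days, and three other readings produce no shortfall. Nor do they support a threat to the main safety or ITT summaries, which do not depend on the minimum. The point deserves correction because it can change who counts as evaluable and which growth visits are tabulated.

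**What to change.** 1. Reconcile Protocol 7.1, 11.3.2 with Table 2, 11.3.2.8 and SAP 6.2.3 (with matching wording in SAP 4.1) to one end-of-dosing definition. It should say whether age is exact or protocol-defined, whether 34w0d or 34w6d is meant, and how a start after the day of birth is counted. This review does not say which rule is right.
2. State the evaluability, replacement and per-protocol thresholds consistently with that definition, so that an infant dosed as the text directs is classified unambiguously.
3. Reconcile the 70% (Protocol) and 75% (SAP) footnotes. Only 70% reproduces the tabled minimums.
4. In SAP 6.2.2, give an explicit formula for the expected last dose date, or count the post-dosing windows from the actual last dose for infants who complete dosing as planned.

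The cost is clarifying wording in the protocol and SAP, with no extra infants.

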### 11.3.3. Post Dosing Assessments

#### *11.3.3.1. 1 Week*

The following procedures will be performed at one week ( $\pm 2$  days) following completion of dosing:

- Physical Examination
- Vital Signs
- Growth Assessment
- Assessment of AEs
- Assessment of concomitant medication changes

#### *11.3.3.2. 1 Month*

The following procedures will be performed between 30 to 35 days following completion of dosing:

- Physical Examination
  - Vital Signs
-

- Growth Assessment
- Assessment of AEs
- Assessment of concomitant medication changes

#### *11.3.3.3. 3 Months*

The following procedures will be performed between 85 and 99 days following completion of dosing:

- Physical Examination
- Vital Signs
- Growth Assessment
- Assessment of AEs
- Assessment of concomitant medication changes

#### *11.3.3.4. 6 Months/End of Study*

The following procedures will be performed between 181 and 195 days following completion of dosing:

- Physical Examination
- Vital Signs
- Growth Assessment
- Assessment of AEs
- Assessment of concomitant medication changes

### **11.4. Early Withdrawal Study Assessments**

For subjects who withdrawal from the study prior to the 6-month post-dosing follow-up, the following procedures will be performed:

- Physical Examination
- Vital Signs
- Growth Assessment
- Assessment of AEs
- Assessment of concomitant medication changes

For subjects who withdrawal from the study prior to the 6-month follow-up assessment, the following procedures will be performed:

- Growth Assessment

## 12. ADVERSE EVENTS

### 12.1. Assessment Period

AEs will be assessed from the time the subject receives their initial dose of study medication through 6 months following the last dose of study drug. All AEs reported during this period, regardless of severity relationship to blinded study treatment, will be recorded.

### 12.2. Definitions

#### 12.2.1. Adverse Event

An **adverse event** (AE) is any untoward medical event associated with the use of a drug in humans, whether or not considered drug-related. An AE can therefore be any unfavorable and unintended sign (including an abnormal laboratory finding, for example), symptom, or disease temporally associated with the use of a drug and does not imply any judgment about causality.

Based upon the above definition of an AE, physical examination findings/abnormalities (inclusive of severity, nature and duration of the finding) that, in the opinion of the principal investigator, are expected to be observed in this patient population would not be considered untoward medical events and do not require reporting as AEs.

An untoward medical event which occurs outside the period of follow-up as defined in the protocol will not be considered an AE. Worsening of a medical condition for which the efficacy of the study drug is being evaluated will not be considered an AE.

#### 12.2.2. Unexpected Adverse Event

An **unexpected adverse event** is an AE that is not listed in the Investigator Brochure (IB) or an AE not listed in the IB at the specificity or severity that has been observed.

For example, under this definition, the AE of **hepatic necrosis** would be considered “unexpected” (by virtue of greater severity) if the investigator brochure had referred previously only to elevated **hepatic enzymes** or **hepatitis**. Similarly, **cerebral thromboembolism** and **cerebral vasculitis** would be considered “unexpected” (by virtue of greater specificity) if the IB listed only **cerebral vascular accidents**. “Unexpected,” as used in this definition, also refers to AEs or suspected adverse reactions that are mentioned in the IB as occurring with a class of drugs or as anticipated from the pharmacological properties of the drug but are not specifically mentioned as occurring with the particular drug under investigation.

#### 12.2.3. Serious Adverse Event

A **serious adverse event** (SAE) is an AE that in the view of either the investigator or sponsor, results in any of the following outcomes:

- Results in death
- Is life-threatening (an event that in the view of either the investigator or sponsor, its occurrence places the patient or subject at immediate risk of death; it does not include an event that had it occurred in a more severe form, might have caused death)
- Requires in-patient hospitalization or prolongation of existing hospitalization

- Is a congenital anomaly or birth defect
- Results in persistent or significant disability/incapacity or substantial disruption of the ability to conduct normal life functions
- Is an important medical event  
An important medical event that may not be immediately life-threatening or result in death or hospitalization but based upon appropriate medical judgment, may jeopardize the patient or may require medical or surgical intervention to prevent one of the other outcomes listed above. Examples of such events are intensive treatment in an emergency room for allergic bronchospasm; blood dyscrasias or convulsions that do not result in hospitalization; or development of drug dependency or drug abuse.

The term “severe” is often used to describe the intensity (severity) of an event; the event itself may be of relatively minor medical significance (such as a severe headache). This is not the same as “serious”, which is based on subject/event outcome or action criteria usually associated with events that pose a threat to a subject’s life or functioning.

In addition to the above definitions of SAEs, all occurrences of confirmed bacteremia will also be considered an SAE (*i.e.*, other important medical event).

#### 12.2.4. Relationship to Study Drug

The Investigator must attempt to determine if an AE is in some way related to the use of the study drug. This relationship should be described based upon the following definitions:

- **Unrelated/Not Related:** The AE is clearly due to causes distinct from the use of the study drug, such as a documented pre-existing condition, the subject’s clinical state, environmental factors, the effect of other concomitant medications or treatments administered.
- **Unlikely:** The AE does not follow a reasonable temporal sequence from administration of the study drug, does not follow a known response pattern to the study drug, and could readily have been due to other causes such as the subject’s clinical state, environmental factors, the effect of other concomitant medications or treatments administered.
- **Possible:** The AE follows a reasonable temporal sequence from administration of the study drug and follows a known response pattern to the study drug, *BUT*, the AE could readily have been produced by the subject’s clinical state, environmental factors, the effect of other concomitant medications or treatments administered.
- **Probable:** The AE follows a reasonable temporal sequence from administration of the study drug and follows a known response pattern to the study drug *AND* cannot be reasonably explained by the subject’s clinical state, environmental factors, the effect of other concomitant medications or treatments administered. The event improves upon discontinuation of the study drug.
- **Definite/Related:** The AE follows a reasonable temporal sequence from administration of the study drug and follows a known response pattern to the study drug. Based on the known pharmacology of the study drug, the event is clearly related to the effect of the study drug. The AE improves upon discontinuation of the study drug and reappears upon repeat exposure.

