## 5.5. Potential Risks and Benefits

Potential risks associated with the administration of STP206 LBP in humans are not fully known. Based upon the results of the Phase 1 adult study, the nature of the product and published clinical reports, possible AEs include the following:

- Nausea
- Vomiting
- Diarrhea
- Flatulence
- Constipation
- Abdominal Pain
- Epigastric pain
- Dysgeusia
- Dry Mouth
- Dehydration
- Fever
- Chills
- Chills
- Diaphoresis
- Infections, including bacteremia
- Feeling hot or cold
- White blood cell count increased
- Dizziness
- Headache
- Anxiety
- Cough
- Nasal congestion
- Oropharyngeal pain

Refer to the STP206 Investigator's Brochure for additional information.

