### 7.1.1. Stopping Criteria

The following stopping events reported to Leadiant will be evaluated by the DSMC to assess whether the events merit a temporary suspension or stopping study enrollment:

- Any death due to an AE assessed to be directly related to the administration of STP206
- Isolation of an STP206 organism from a normally sterile site (including bacteremia but excluding peritonitis in association with intestinal necrosis) in any subject

All reports of stopping events will be forwarded to the DSMC for review. If either of the above events occurs, enrollment will be suspended temporarily while the DSMC is evaluating the event. Subjects on blinded study drug will continue dosing during the assessment of the event.

If a stopping criterion is met, the DSMC will perform an unblinded review of the event to assess causality and its overall impact on subject safety and provide its recommendations to Leadiant. If an event, in the opinion of the DSMC, is related to the administration of STP206, dosing of all ongoing study subjects will be halted, and the study will be suspended temporarily. FDA will be notified of all DSMC's recommendations before taking any actions with the study.

A flow diagram for the process of evaluating infections of normally sterile sites that are suspected to be associated with STP206 organisms (*i.e.*, gram positive bacilli) is provided in [Appendix E](#).

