## 7.7. Study Monitoring Committees

An independent DSMC will be used to review data generated in this study, provided as a separate document. A [Charter](#) for the DSMC outlining the membership, roles and responsibilities was developed and finalized prior to the initiation of the study and submitted to the FDA on 03 December 2013 (SN 0030).

Available data on primary and secondary endpoints, including AEs, will be included in each review. The DSMC can give recommendations regarding continuation of study, temporary hold on study while additional data is further analyzed, or termination of the study. The DSMC will also review events that may constitute stopping criteria (see [Section 7.1.1](#)) on an as needed basis. Unscheduled DSMC review of study data may occur at any time on an as-needed basis if requested by the DSMC.

The DSMC will review data for each dose/birth weight group to assess whether proceeding to lower birth weight and/or higher STP206 doses is warranted. Data reviewed at each DSMC meeting will follow the following schedule:

- For the first group of subjects (Study Group 1a – Birth weight 2000 to 1501 g and low dose STP206), data will be reviewed through the completion of dosing.
- For the next six DSMC reviews (Study Groups 1b through 4a), data the current dose group will be reviewed through the completion of dosing along with 30-day post dosing data from the prior dose group.
- For the final DSMC review (Study Group 4b), data through 30-days post dosing will be reviewed.

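### Protocol 12.2.4 leaves some adverse events with no causality category: plausibly timed events with no known pattern, and fatal events that never improved and have no other explanation

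*Protocol*

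**What the plan says.** Protocol 12.2.4 gives the investigator a five-step causality scale. Possible, Probable and Definite/Related all start from the same two conditions, timing and pattern: "The AE follows a reasonable temporal sequence from administration of the study drug and follows a known response pattern to the study drug". They then differ:

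- Possible requires that something else could readily account for the event.
- Probable requires that nothing else reasonably explains it, and adds "The event improves upon discontinuation of the study drug".
- Definite/Related requires a clear link through the drug's pharmacology, and adds "The AE improves upon discontinuation of the study drug and reappears upon repeat exposure".

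The definition of Unlikely begins "The AE does not follow a reasonable temporal sequence from administration of the study drug, does not follow a known response pattern", and it also requires a ready alternative cause. Not Related is for events clearly due to something else. No exception is made for events that are fatal, irreversible or not seen before.

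The ratings feed the analysis. Protocol 13.2.3.2 counts Possible, Probable and Definite as related. SAP 8.7.2 plans tables of related AEs, overall and at Grade 3.

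The death stopping criterion in Protocol 7.1.1 also turns on causality: "Any death due to an AE assessed to be directly related to the administration of STP206". The adverb *directly* corresponds to no step of the 12.2.4 scale, and 7.1.1 does not say whose assessment governs. The section continues: "If a stopping criterion is met, the DSMC will perform an unblinded review of the event to assess causality".

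**The concern.** A causality scale should give every event a place and should rank stronger evidence above weaker. This one makes prior knowledge of the drug's effects a condition of every related rating, in a population where that knowledge is thin. Protocol 5.5 says so: "Potential risks associated with the administration of STP206 LBP in humans are not fully known". According to 5.3.2.2, no trial of STP206 for NEC prevention in neonates preceded this one. The STP206 experience described in 5.3.2.1 is 17 healthy adults dosed for at most seven days, with no serious events. Table 2 plans up to 77 days of dosing in neonates. Section 12.2.2 defines unexpected AEs, so the protocol foresees events outside the known profile, yet 12.2.4 offers a plausibly timed one no related rating.

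Two things are at stake. The related-AE tables could omit the events that a first study in this population most needs to show, or sites could fill the gap in different ways. And if the death criterion in 7.1.1 relies on the same ratings, a missing or low rating could keep the criterion from being met. The unblinded causality review described there follows only once it is met.

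**Working it through.** The plan states no figure to reproduce, so the check is to apply each definition in turn. The attributes, all from 12.2.4, are plausible timing, known pattern, ready alternative cause, improvement off drug, return on re-exposure, and a clear link by pharmacology. Not Related is set aside because it needs an event clearly due to another cause. I treat the alternative-cause conditions of Possible and Probable as opposites. The wording leaves some middle ground between them, which would only add unclassified cases.

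For an event with plausible timing:

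| Event | Unlikely | Possible | Probable | Definite |
|---|---|---|---|---|
| Fatal, never improved; known pattern; ready alternative cause | No: timing is plausible | Yes | No: no improvement | No: no improvement or return |
| Fatal, never improved; known pattern; no alternative cause | No: timing is plausible | No: needs an alternative cause | No: no improvement | No: no improvement or return |
| No known pattern, whatever else is true | No: timing is plausible | No: needs the pattern | No: needs the pattern | No: needs the pattern |
| Improved off drug, returned on re-exposure, then fatal; known pattern; no alternative cause | No: timing is plausible | No: needs an alternative cause | Yes | Yes, if the pharmacology condition is also met |

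Counting the combinations:

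- Fatal, never improved: pattern, alternative cause and pharmacology can each be yes or no, giving 2 × 2 × 2 = 8 combinations. Two reach a category (Possible: known pattern with an alternative cause, pharmacology either way). The other six reach none. Ignoring pharmacology, that is 1 of 4.
- No known pattern: alternative cause, improvement, return and pharmacology give 2 × 2 × 2 × 2 = 16 combinations. None reaches a category.

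These are counts of logical cases, not frequencies. The documents give no rate from which to estimate how many events would be affected.

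Rows 1 and 2 show the order reversing: removing the competing explanation strengthens the causal case but takes the event from Possible to no category.

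The re-exposure condition also sits awkwardly with Protocol 10.8.2. After suspected sepsis or sterile-site infection, that section lets dosing resume only if cultures show no gram-positive bacilli or STP206 organisms are not confirmed. A confirmed STP206 infection would therefore not ordinarily receive the re-exposure that Definite requires. The two sections need to be read together and reconciled.

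For the analysis, an event without a category cannot be counted as related by its definition. SAP 8.7.2 has a row for missing relationship, so such an event could appear there, or under whichever category the site chose. Separately, SAP 8.7.2 names only Possible and Probable as related, while Protocol 13.2.3.2 includes Definite.

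**The case against.** The strongest reply is that little depends on this scale alone. Much of that stands.

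- **Stopping and oversight.** Protocol 12.4 requires all serious events to be reported whatever their relationship, fatal ones at once, and the sponsor's medical monitor evaluates each. Each cohort opens only after DSMC review. Section 7.7 adds "The DSMC will also review events that may constitute stopping criteria", permits unscheduled reviews, and lets the DSMC recommend a hold or termination. The other stopping event, isolation of an STP206 organism from a normally sterile site, needs no causality rating.
- **Signal detection.** The primary endpoint compares the incidence and severity of AEs and SAEs with control, not related events. The SAP tabulates all treatment-emergent AEs, Grade 3 events, SAEs, events leading to discontinuation or death, and hospital mortality, by arm.
- **Known pattern.** The condition is not empty. Section 5.5 lists possible AEs, including infection and bacteremia, and refers to the Investigator's Brochure, which was not available here.
- **Judgement.** Section 12.2.4 asks the investigator to try to determine whether an event is in some way related, so judgement is not excluded. It also says to describe the relationship by these definitions, so different sites may bridge the gap differently.

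A reader might infer three stronger conclusions that the documents do not support:

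- That no fatal event can be Probable or Definite. Dosing can be suspended and restarted, and the last row of the table shows a route to both.
- That new toxicities are forced into Unlikely. Unlikely requires implausible timing, so a plausibly timed new event is unclassified instead.
- That the death criterion can never be met. Section 7.1.1 does not cite 12.2.4, and its key term is undefined. The DSMC charter is a separate document, and the flow diagram in Appendix E is not in the text reviewed; either may deal with this.

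**Conclusion.** The gap in 12.2.4 is real on the wording. Plausibly timed events with no known pattern fit none of Unlikely, Possible, Probable or Definite. Fatal events that never improved and have no alternative explanation fit none either, while a weaker case of the same event can be Possible. The related-AE tables under Protocol 13.2.3.2 and SAP 8.7.2 can therefore miss such events or classify them inconsistently.

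The effect on stopping is conditional. It requires reading the causality term in 7.1.1 on the 12.2.4 scale. That is the only causality scale in the two documents, but the link remains an inference. Even on that reading, the safeguards above limit the loss without repairing the definitions. A fatal toxicity that yields no STP206 isolate has no stopping trigger of its own free of a causality judgement, and would depend on DSMC review.

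The conclusion rests on a literal reading of the definitions. It is a wording correction worth making, not a failure of the trial's safety monitoring.

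**What to change.** In Protocol 12.2.4, make a known response pattern supportive evidence rather than a requirement, at least for Possible. Qualify the improvement and re-exposure conditions with *where assessable*, so that a fatal or irreversible event is not excluded by its outcome.

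Reconcile the causality term in 7.1.1 with the 12.2.4 categories, and make clear whose assessment applies. Which ratings should trigger the criterion is for the sponsor and the DSMC to settle. In the same revision, align SAP 8.7.2 with Protocol 13.2.3.2 on Definite/Related.

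The cost is amended wording. Somewhat more AEs will be rated Possible. Because ratings are made blinded, this should apply in both arms. Ratings already made under the existing definitions should be identified as such in the report.
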